PROTOCOL TITLE:

A Prospective Randomized Evaluation of Two Perioperative Active Warming Techniques in Maintenance of Normothermia in Colorectal Surgeries

PRINCIPAL INVESTIGATOR:

[name]. Department of Anesthesiology [contact] [contact]

CO-INVESTIGATOR

[name]. Department of Anesthesiology [contact] l- [contact]

VERSION NUMBER: 1.1

VERSION DATE: 12.12.2017

Industry Clinical Trial: VitaHeat Medical, Inc.

Table of Contents

1.0	Objectives	3
2.0	Background	3
3.0	Inclusion and Exclusion Criteria	3
4.0	Study-Wide Number of Subjects	3
5.0	Study-Wide Recruitment Methods	3
6.0	Multi-Site Research	4
7.0 St	tudy Timelines	4
8.0 S	tudy Endpoints	4
9.0	Procedures Involved	4
10.0	Data and Specimen Banking	5
11.0	Data and Specimen Management	5
12.0	Provisions to Monitor the Data to Ensure the Safety of Subjects	6
13.0	Withdrawal of Subjects*	6
14.0	Risks to Subjects*	6
15.0	Potential Benefits to Subjects	7
16.0	Vulnerable Populations.	7

Page 1 of 19

17.0	Community-Based Participatory Research	7
18.0	Sharing of Results with Subjects	8
19.0	Setting	8
20.0	Resources Available	8
21.0	Prior Approvals	9
22.0	Recruitment Methods	9
23.0	Local Number of Subjects	9
24.0	Confidentiality	10
25.0	Provisions to Protect the Privacy Interests of Subjects	
26.0	Compensation for Research-Related Injury	10
27.0	Economic Burden to Subjects	10
28.0	Consent Process	10
29.0	Process to Document Consent in Writing.	13
30.0	Budget	14
31.0	Drugs or Devices.	14
32.0	Financial Disclosure	14

1.0 **Objectives**

We propose a study in which we compare two intraoperative active warming devices for maintenance of normothermia in patients undergoing colorectal surgery. A novel underbody resistive warming mattress (VitaHeat Medical) will be compared to the forced air warming blanket (3M Bair Hugger) that is currently used in our institution.

Our hypothesis is that the underbody resistive warming mattress will be equally effective as forced air warming in maintaining normothermia in colorectal surgery.

2.0 **Background**

In humans, maintenance of core temperature is tightly regulated by the thermoregulatory center in the hypothalamus. However, skin temperature varies in differing ambient temperatures due to continuous heat transfer. Heat transfer from the body to the environment occurs by convection, conduction, radiation and evaporation. (1)

Upon induction of anesthesia thermoregulatory control is impaired which results in a significant redistribution of core body heat to the periphery resulting in hypothermia. During anesthesia, skin surface is responsible for majority of heat loss. This occurs mainly by radiation and convection (90%) and to a lesser degree by evaporation and conduction (5% each). (2)

Hypothermia is recognized as an important risk factor in the development of various perioperative complications. Hypothermia induced coagulation abnormality increases perioperative blood loss, leading to increased need for blood transfusions. Other important complications are surgical site infections, myocardial injury, and longer length of hospital stay. In fact, perioperative hypothermia has been identified as an independent risk factor for surgical site infections (SSI). (2)

Page 2 of 19 Revised Template: December 12, 2017

Colorectal surgery is associated with higher risk of SSI's than most other surgeries. In these surgeries, maintenance of intraoperative normothermia, defined as temperature above 36°C, may be particularly challenging. Contributing factors to hypothermia include long duration of surgery, extensive surgical exploration, and patient positioning. Despite the availability of many warming techniques, many surgical patients still exit the operating room hypothermic. Reducing perioperative hypothermia could greatly reduce morbidity and mortality in colorectal surgery.

Devices and methods that are available for prevention of intraoperative hypothermia can be grouped into passive and active warming.

Passive warming with insulating blankets (cotton or reflective) reduce heat loss by only 30% (2) and obviously cannot be used alone to maintain normothermia.

Active warming methods that are most effective are convective and conductive warming. Forced air warming has been the standard of care for skin surface warming with many studies showing its effectiveness. It is convective heat transfer that relies on the amount of exposed skin surface. The efficacy of forced air is decreased when skin surface area is limited due to surgical reasons and positioning. Temperature gradient from the hose to the periphery exists makes distribution of heat uneven. Burn injuries have been reported when the hose was used alone against manufacturer's guidelines (4).

Another group of warming devices are circulating—water garments. These are devices that have warm water circulating through a conductive-heating garment that is wrapped around the patient. It has been shown to be more effective in heat transfer than forced air warming (5) and more effective in patients undergoing abdominal surgery. (6) However, potential for leakage, difficulty with handling and higher maintenance costs are limiting factors.

Circulating water and electrical mattresses placed under the patient have been ineffective in maintaining normothermia. (7)

Radiant heaters such as incubators for neonates are used most commonly in neonates. Radiators may be used at a safe fixed distance. At this distance the efficacy of radiant heat is less than forced air warming. (8) Also a high risk of burn injury exists if this safe distance is not maintained.

Fluid warming (to near 37° C) alone is not effective in maintaining normothermia. However, in patients undergoing major surgeries where more than 1 L/hour of fluid is administered intraoperatively the combination with other warming techniques have been shown to be more effective than the warming device alone. (9)

Resistive heating devices have been shown to be comparable to forced air in preventing intraoperative hypothermia. They are multi-part devices controlled by a

Page 3 of 19 Revised Template: December 12, 2017

A Prospective Randomized Evaluation of Two Perioperative Active Warming Techniques for Maintenance of Normothermia in Colorectal Surgeries central unit making them bulky. Due to their size, cleaning and maintenance may be costly. (10)

VitaHeat is an FDA approved novel underbody conductive heating mattress that uses resistive heating technology. This device overcomes some of the deficiencies of the older resistive devices. Some of the improved features include silent operation, ease of cleaning, reusability and low maintenance.

In this study, we will compare the efficacy of this new warming device to the standard warming technique in patients undergoing colorectal surgery under general anesthesia.

References:

- 1. Sessler DI Perioperative thermoregulation and heat balance. Lancet 2016; published online on Jan16, 2016
- 2. Torosian A Thermal management during anaesthesia and thermoregulation standards for the prevention of inadvertent perioperative hypothermia. Best Pract Research Clin Anaesth 2008; 22: 659-668.

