3.0 Inclusion and Exclusion Criteria

- 3.1 All patients' ≥18 years of age who are scheduled to undergo laparoscopic or open colorectal surgical procedures under general anesthesia are eligible to participate.
- 3.2 **Inclusion:** Eligible subjects will include patients 18 years of age undergoing laparoscopic or open colorectal surgical procedures under general anesthesia.

Exclusion: Patients less than 18 years of age, emergent surgery, thyroid problems, preoperative fever and pregnant patients.

- Adults unable to consent: *Exclude*
- Individuals who are not yet adults (infants, children, teenagers): *Exclude*
- Pregnant women: *Exclude*
- Prisoners: Exclude
- 4.0 Study-Wide Number of Subjects: N/A
- 5.0 Study-Wide Recruitment Methods: N/A
- 6.0 Multi-Site Research: N/A
- 7.0 **Study Timelines**
 - 7.1 Describe:
 - The duration of an individual subject's participation in the study: 30 days
 - The duration anticipated to enroll all study subjects.12/31/2018

 ☐ The estimated date for the investigators to complete this study (complete primary analyses).03/01/2019.

8.0 **Study Endpoints**

- 8.1 The primary outcome measure will be the percentage of intraoperative time above a body temperature of 36°C.
- 8.2 The secondary outcomes will be the amount of blood or blood product transfusion, surgical site infections as defined by National surgical quality improvement project (NSQIP) and other infections such as urinary tract infections, pneumonias, cardiac events such as cardiac arrest and myocardial infarction, thromboembolic complications (DVT/PE). Length of hospital stay will be recorded as will length of stay, time to return of bowel function (time to first flatus) will be recorded. At 30 days following

Page 5 of 19 Revised Template: December 12, 2017

the surgery readmissions to the hospital, the reason for the admission and the length of stay during this additional hospitalization will be recorded.

9.0 **Procedures Involved**

9.1 Study design: A prospective randomized controlled trial.

Stratified randomization will be performed using a computerized randomization table where the strata will be type of surgery (open vs closed) and the treatment will be forced air blanket or underbody mattress warming device. This will allow equal groups of both warming devices in both types of surgery.

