10.0 Data and Specimen Banking: N/A

11.0 Data Analysis and Management

The primary outcome measure will be the percentage of intraoperative time above a body temperature of 36° C. Melton GB at el. reported the absolute percentage of time above

Page 7 of 19 Revised Template: December 12, 2017

A Prospective Randomized Evaluation of Two Perioperative Active Warming Techniques for Maintenance of Normothermia in Colorectal Surgeries the threshold of 36 °C was 57% in patients receiving standard forced air warming intraoperatively. (10)

The number of subjects (N=146) was determined for two groups of 73 in each group to achieve 83% power to detect a difference of 10% between the active warming underbody mattress and forced air warming device, assuming that the standard forced air warming method would achieve a value of 57% and that non-inferiority would be set as a marginal difference of -10%. This sample would provide a significance level of 0.042 using a onesided Z test. Seven patients will be added to each group for protocol violations and data lost in follow up making 160 the total number of subjects that will be recruited.

Interim analysis is preplanned with two looks at n=74 and n=146. Significance and futility boundaries for look 1 and 2 are set at:

Boundaries for Scenario 1

	Significanc	e Boundary	Futility Boundary	
	Z-Value	P-Value	Z-Value	P-Value
Look	Scale	Scale	Scale	Scale
1	2.72119	0.00325	0.16669	0.43381
2	1.54065	0.06170	1.54065	0.06170

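### Section 1.0 hypothesises equal effectiveness, but the only decision rule (11.0) is one-sided non-inferiority at -10 points, and a pass there cannot show equality

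*Combined protocol and SAP*

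**What the plan says.** Section 1.0 (Objectives) gives the hypothesis: "Our hypothesis is that the underbody resistive warming mattress will be equally effective as forced air warming in maintaining normothermia in colorectal surgery". Section 8.1 gives the endpoint: "The primary outcome measure will be the percentage of intraoperative time above a body temperature of 36°C". This is one percentage per patient, so the comparison is between two means.

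Section 11.0 gives the test. Its sample-size sentence assumes that "the standard forced air warming method would achieve a value of 57% and that non-inferiority would be set as a marginal difference of -10" percent, and adds: "This sample would provide a significance level of 0.042 using a onesided Z test". The design has two looks, at n=74 and n=146, with a printed final boundary of Z = 1.54065 (one-sided p = 0.06170).

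The plan contains no equivalence test and no upper margin. It gives no reason for choosing 10 points, no SD for the endpoint, and no statement of how a positive result will be worded.

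**The concern.** The hypothesis and the test answer different questions. Equal effectiveness is a two-sided claim that the devices do not differ by an amount that matters in either direction. The test in 11.0 asks only whether a loss of 10 points or more can be excluded. A mattress that is somewhat worse can pass it.

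No conclusion wording is fixed anywhere, so the sentence in 1.0 is the only text that tells a reader what success would mean. If it were carried into a report, the trial would claim more than its test can support. The claim should be settled before data are seen, not least because section 32.0 discloses that the responsible investigator sits, paid, on the sponsor's Scientific Advisory Board.

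**Working it through.** **Inputs from 11.0.** Margin -10 points; 73 evaluable patients per group; forced air assumed at 57%; stated one-sided level 0.042; final boundary Z = 1.54065; first-look boundary Z = 2.72119 at n=74 (37 per group if balanced). **Assumption:** the SD, shown over a range because the documents give none.

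**The plan's own sample size.** Without an SD, the natural working model is binary:

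n per group = (z_α + z_β)² × [p₁(1-p₁) + p₂(1-p₂)] / (true difference + margin)², with z_β = 0.954 for 83% power.

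- Mattress truly 67%, forced air 57%, z_α = 1.54065: 2.495² × (0.2451 + 0.2211) / 0.20² = 72.5, so 73. This reproduces the plan.
- The same with the stated level 0.042 (z_α = 1.728): 83.8, so 84. This does not reproduce it.
- True equality at 57%, level 0.042: 2.682² × 0.4902 / 0.10² = 352.6, so 353.

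The printed boundary therefore fits the planned size and the stated 0.042 does not. I use the boundary below and show the stated level beside it.

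**What a pass means.** The rule is (d + 10)/SE > z, where d is the observed mattress mean minus the forced-air mean and SE = SD × √(2/73) = 0.1655 × SD. A pass therefore requires

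d > -10 + z × 0.1655 × SD.

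| Assumed SD | Smallest passing d, z = 1.54065 | Smallest passing d, z = 1.728 (level 0.042) |
|---|---|---|
| 20 | -10 + 5.10 = -4.90 | -4.28 |
| 25 | -10 + 6.38 = -3.62 | -2.85 |
| 30 | -10 + 7.65 = -2.35 | -1.42 |
| 35 | -10 + 8.93 = -1.07 | about 0 |
| 40 | -10 + 10.20 = +0.20 | +1.44 |
| 49.5 | -10 + 12.62 = +2.62 | +4.16 |

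The last row is the largest SD that a percentage with mean 57 can have: √(57 × 43) = 49.5. The sign changes where z × 0.1655 × SD = 10, that is, at SD = 10/0.2550 = 39.2 for the printed boundary and 35.0 for the stated level.

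**First look.** √(2/37) = 0.2325, so a pass needs d > -10 + 2.72119 × 0.2325 × SD = -10 + 0.633 × SD. This is negative only if the SD is below 15.8. A pass with the mattress observed worse is therefore mainly a matter for the final look.

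**Reading the result against 1.0.** At SD 20, an observed deficit just under 4.9 points passes. The passing statement is that the deficit is less than 10 points. Nothing in the rule limits it to a smaller value, and no second test does so.

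**The case against.** The strongest reply is that 11.0 names the test as non-inferiority and states its margin openly, so the sentence in 1.0 is loose wording and not a false claim. Much of that stands. A reader might infer that a positive result is bound to be over-claimed. The documents do not support this, because they prescribe no conclusion; the risk arises only if the wording of 1.0 is reused.

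A reader might also infer that the rule is lax, passing too readily when forced air performs very badly or almost perfectly. Under the printed two-look boundaries and the maximum-variance model, two identical devices are declared non-inferior in 36% of trials at 57%, 67% at 10% or 90%, and 88% at 5% or 95%. But those are correct declarations, that is, power at a true difference of zero. A mattress truly on the margin (47% against 57%, or 80% against 90%) passes only about 6% of the time. Nothing in the documents suggests that forced air will reach either extreme, and the margin is stated in the same sentence as the 57%.

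Section 2.0 does say "The efficacy of forced air is decreased when skin surface area is limited due to surgical reasons and positioning" and "Circulating water and electrical mattresses placed under the patient have been ineffective in maintaining normothermia". It also says that resistive devices have proved comparable to forced air, that many studies support forced air, and that passive warming cannot suffice alone. It does not establish that the comparator would fail here, or that an unwarmed arm was needed.

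Finally, requiring forced air to reach 57% before any claim would not be a sound safeguard. That figure is a planning mean, not a threshold for a working comparator. Suppose the claim were blocked when the forced-air 95% interval lay wholly below 57%, and forced air truly gave 50%. The block would apply below an observed mean of 57 - 1.96 × 35/√73 = 49.0 at SD 35, or 52.4 at SD 20. That is about 40% and 85% of trials respectively, whatever the mattress did.

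**Conclusion.** The mismatch stands: passing 11.0 cannot establish the hypothesis in 1.0. It establishes only that the mattress is not worse by 10 percentage points or more of mean intraoperative time above 36°C.

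The practical size rests on an SD that the documents do not give. Below about 39 points (about 35 at the stated 0.042), the trial can pass with the mattress observed worse, by up to 4.9 points at SD 20 and 1.1 at SD 35. At the maximum variance for 57%, a pass needs the mattress about 2.6 points ahead.

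A reader who sees the planned size reproduced with the mattress at 67% might conclude that the design presumes a better mattress. That follows only in the binary model. With a continuous endpoint, 73 per group gives 83% power at true equality if the SD is about 22.5 (stated level) or 24.2 (printed boundary). The power assumptions and the disagreement between 0.042 and the printed boundary need their own answer; this point does not depend on it.

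**What to change.** In 1.0, restate the hypothesis, and state in 11.0 that the permitted conclusion is the same: *the mattress is not worse than forced air by more than 10 percentage points of mean intraoperative time above 36°C*.

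In 11.0, add that both arm means will be reported with their difference and its confidence interval, so that the fixed margin can be read against the forced-air level actually observed. State the confidence level. The printed final boundary corresponds to a one-sided 93.83% bound (1 - 0.0617), so a conventional 95% interval can cross -10 after a pass. At SD 20 and d = -4.9, for example, it is -4.9 ± 1.96 × 3.31, or -11.4 to +1.6. A sentence justifying the choice of 10 points would complete the change.

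The cost is protocol wording and a summary of data already collected; the sample size need not change for this point. Keeping the equality claim and testing it would be far dearer. Equivalence within ±10 points, at 57% in both arms, 0.042 per side and 83% power, needs 0.4902 × (1.728 + 1.372)² / 0.01 = 471.1, so about 472 per group in the binary model. With 73 per group, power would be about 51% at SD 25 and 23% at SD 30.

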3.0 Inclusion and Exclusion Criteria

- 3.1 All patients' ≥18 years of age who are scheduled to undergo laparoscopic or open colorectal surgical procedures under general anesthesia are eligible to participate.
- 3.2 **Inclusion:** Eligible subjects will include patients 18 years of age undergoing laparoscopic or open colorectal surgical procedures under general anesthesia.

Exclusion: Patients less than 18 years of age, emergent surgery, thyroid problems, preoperative fever and pregnant patients.

- Adults unable to consent: *Exclude*
- Individuals who are not yet adults (infants, children, teenagers): *Exclude*
- Pregnant women: *Exclude*
- Prisoners: Exclude
- 4.0 Study-Wide Number of Subjects: N/A
- 5.0 Study-Wide Recruitment Methods: N/A
- 6.0 Multi-Site Research: N/A
- 7.0 **Study Timelines**
 - 7.1 Describe:
 - The duration of an individual subject's participation in the study: 30 days
 - The duration anticipated to enroll all study subjects.12/31/2018

 ☐ The estimated date for the investigators to complete this study (complete primary analyses).03/01/2019.

8.0 **Study Endpoints**

- 8.1 The primary outcome measure will be the percentage of intraoperative time above a body temperature of 36°C.
- 8.2 The secondary outcomes will be the amount of blood or blood product transfusion, surgical site infections as defined by National surgical quality improvement project (NSQIP) and other infections such as urinary tract infections, pneumonias, cardiac events such as cardiac arrest and myocardial infarction, thromboembolic complications (DVT/PE). Length of hospital stay will be recorded as will length of stay, time to return of bowel function (time to first flatus) will be recorded. At 30 days following

Page 5 of 19 Revised Template: December 12, 2017

the surgery readmissions to the hospital, the reason for the admission and the length of stay during this additional hospitalization will be recorded.

9.0 **Procedures Involved**

9.1 Study design: A prospective randomized controlled trial.

Stratified randomization will be performed using a computerized randomization table where the strata will be type of surgery (open vs closed) and the treatment will be forced air blanket or underbody mattress warming device. This will allow equal groups of both warming devices in both types of surgery.

Group 1: Patients will receive active warming via a heating mattress (VitaHEAT Medical) placed on the OR table with two thin sheets between the patient and the device; one covering the mattress and the other used as the draw sheet as usual practice. The device will be turned on 10 minutes prior to the patients' arrival to the operating room table. Patients' upper body will be covered with blankets. To increase skin surface contact with the mattress any blankets remaining under the patients' chest or head will be removed after intubation and replaced with a donut.

Group 2: Patients will receive standard forced air warming applied to the upper body and turned on after the patient is prepped and draped. These warmers will be placed directly in contact with the skin without any intervening insulation.

Both groups will have IV fluid warmer initiated on arrival to the operating room. The operating room temperatures will be adjusted to 21° C.

Participation in the study is voluntary. The patients may choose not to enroll in the research. Patients who choose not to enroll will use the standard forced air warmer.

Preoperative and postoperative temperatures will be measured orally. Intraoperative core and skin temperatures will be monitored continuously at 1 minute intervals using an esophageal probe and skin temperature probe using a skin temp probe placed on the great toe and covered to prevent any contact with the warming devices.

The total amount of gas flows will be maintained at 2 L/min. Total and fractional inspired concentration of oxygen (FiO₂) will be maintained 60% in both groups except for the periods of induction and emergence.

A heating mattress (VitaHEAT Medical) will be used as the research device in this study. The mattress has regulatory approval. This heating mattress (VitaHEAT Medical) is a reusable underbody conductive warming mattress which heats to a maximum of 41°C. This device will be compared to the forced air warming which heats to a maximum of 43°C. It meets all FDA safety guidelines.

Temperatures that will be record are:

Operating room temperatures will be collected at three different times:

Page 6 of 19 Revised Template: December 12, 2017

- 1. upon arrival of the patient to the operating room using a calibrated thermometer
- 2. at incision
- 3. at extubation.

Patient temperatures will be recorded at:

- 1. In the preoperative area (orally)

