Pre-Op Temp (Oral)	Surgery Type (Circle):
Temp upon arrival to ASU: Time:	Open
Temp at transfer from ASU:Time:	Laparoscopic
Epidural :	Heparin Pre-Op:
Yes / No (Circle Answer)	Yes / No (Circle Answer)
ANESTHESIA PROVIDER: PLEAS	SE COMPLETE BELOW
PATIENT Intra-Op Temp	Patient Position (Circle):
(Core and Skin)	Supine
Ensure that EMR is recording patient	Lithotomy
temperatures at intervals of 1 minute	·
Operating Room Temp	Arm position (Circle):
OR Room temp (upon patient arrival):	On arm boards
OR Room temp (at time of incision):	Tucked
OR Room temp (at time of extubation):	
Warming Device Used (Circle):	Presence of posterior skin
Bair Hugger	surface injury: (for burn injury)
VitaHEAT	
Fluid warmer	Yes No
	If Yes describe:
Anesthesiologist (Print Name):	

Page 14 of 19 Revised Template: December 12, 2017

PACU DATA SHEET

Post-Op Temp (Oral)		Warming Device Used (Circle):
Temp at admission:	Time:	Bair Hugger
Temp at discharge:	Time:	Fluid warmer

Abdominal Surgery Normothermia Patient De-identifier Code List

			illa i atient be-identifier e	
Case	Name	Date of Surgery	Medical Record Number	Telephone #
1				
2				
3				
4				
5				
6				
7				
8				
9				
10				
11				
12				
13				
14				
15				
16				
17				
18				

Page 15 of 19 Revised Template: December 12, 2017

19 20 21 22 23 24 25 26 27	
21 22 23 24 25 26 27	
22 23 24 25 26 27	
23 24 25 26 27	
24 25 26 27	
25 26 27	
26 27	
27	
28	
29	
30	
31	
32	
33	
34	
35	
36	
37	
38	
39	
40	
41	

Page 16 of 19

Revised Template: December 12, 2017

42 43 44 44 45 46 47 48 49 50 51 52 53 54 55 56 57 58 59 60 61 62 63 64 65 65	100111119	 1 (011110 011011	ina in Colorectal Burgeries	
44 45 46 47 48 49 50 51 52 53 54 55 56 57 58 59 60 61 62 63 64	42			
45 46 47 48 49 50 51 52 53 54 55 56 57 58 59 60 61 62 63 64	43			
46 47 48 49 50 51 52 53 54 55 56 57 58 59 60 61 62 63 64	44			
47 48 49 50 51 52 53 54 55 56 57 58 59 60 61 62 63 64	45			
48 49 50 51 52 53 54 55 56 57 58 59 60 61 62 63 64	46			
49 50 51 52 53 54 55 56 57 58 59 60 61 62 63 64	47			
50 51 52 53 54 55 56 57 58 59 60 61 62 63 64	48			
51 52 53 54 55 56 57 58 59 60 61 62 63 64	49			
52 53 54 55 56 57 58 59 60 61 62 63 64	50			
53 54 55 56 57 58 59 60 61 62 63 64	51			
54 55 56 57 58 59 60 61 62 63 64	52			
55 56 57 58 59 60 61 62 63 64	53			
56 57 58 59 60 61 62 63 64	54			
57 58 59 60 61 62 63 64	55			
58 59 60 61 62 63 64	56			
59 60 61 62 63 64	57			
60 61 62 63 64	58			
61 62 63 64	59			
62 63 64	60			
63 64	61			
64	62			

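### Allocation is stratified by open vs closed surgery, but the plan never says whether that stratum enters the primary analysis; with balance within strata and a prognostic surgery type, a plain two-group test is conservative

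*Combined protocol and SAP*

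**What the plan says.** Section 9.1 sets up the allocation: "Stratified randomization will be performed using a computerized randomization table where the strata will be type of surgery (open vs closed"). It gives the purpose as well: "This will allow equal groups of both warming devices in both types of surgery". It does not mention blocks.

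Section 8.1 defines the endpoint, one value per patient: "The primary outcome measure will be the percentage of intraoperative time above a body temperature of 36°C".

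Section 11.0 is the only analysis text. It sizes the trial at 73 per group for 83% power with a margin of -10%, "assuming that the standard forced air warming method would achieve a value of 57"%. The one test it names is in that same paragraph: "This sample would provide a significance level of 0.042 using a onesided Z test". It then adds: "Interim analysis is preplanned with two looks at n=74 and n=146", prints the boundaries, and turns to data storage. It mentions no stratum, covariate, model or variance estimator. Section 33.0 says only that the department statistician does the analysis.

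The data collection form has a field "Surgery Type (Circle") offering open or laparoscopic. It does not say whether the planned or the performed type is meant.

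**The concern.** When allocation is balanced within strata, differences between the strata cancel out of the arm comparison. A plain two-group standard error still counts them as noise. If surgery type is prognostic, that standard error is too large, the true one-sided error falls below nominal, and the non-inferiority interval is wider than it need be at both looks.

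A prognostic effect is plausible. Section 2.0 says: "Contributing factors to hypothermia include long duration of surgery, extensive surgical exploration, and patient positioning". It does not say that open and laparoscopic cases differ on these, so the effect is not documented.

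The second issue is the open choice. Adjusted and unadjusted results can fall on different sides of the -10 margin, and nothing fixes which one counts before data are seen, including at the first look.

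**Working it through.** **Inputs from section 11.0.** 73 per arm, margin 10 points, one-sided 0.042 (z = 1.728), forced-air value 57%, looks at 37 and 73 per arm, boundaries Z 2.72119 (futility 0.16669) and then 1.54065.

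**Assumed, because the documents give no figure.**
- Total SD of 22.5-49.5 points. The upper end is the largest SD that a 0-100 outcome with mean 57 can have: 100 × √(0.57 × 0.43) = 49.5. The lower end is the SD that reproduces the plan, as shown next.
- Share of open cases p of 0.2-0.5.
- Gap d between surgery types of 0, 10, 20 or 30 points.

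**Reproducing the plan's figure.** With k = √(2/73) = 0.1655, a comparison of means at true equality has power Φ(10/(SD·k) − 1.728). At SD 22.5 this is Φ(10/3.724 − 1.728) = Φ(0.957) = 83.1%, which matches the stated 83%. The plan does not state this SD.

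**Formulas.** Between-stratum variance B = p(1−p)d²; within-stratum SD s = √(SD² − B).
- Power with the stratum: Φ(10/(s·k) − 1.728)
- Power of the plain test, arms balanced within strata: Φ((10 − 1.728·SD·k)/(s·k))
- True one-sided error of the plain test: 1 − Φ(1.728·SD/s)
- Power of the plain test, no balancing within strata: Φ(10/(SD·k) − 1.728)

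**Worked case: SD 30, d = 20, p = 0.2.** B = 0.16 × 400 = 64; s = √836 = 28.91; s·k = 4.786; SD·k = 4.966.
- With the stratum: Φ(2.090 − 1.728) = 64.1%
- Plain test: Φ((10 − 8.580)/4.786) = Φ(0.297) = 61.7%
- Error of the plain test: 1 − Φ(1.793) = 0.036

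At SD 49.5 with the same gap and share, power goes from 30.4% to 31.2%.

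**Over the whole range, at true equality:**

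| Gap | B as share of variance | Gain, single test (points) | True error of plain test | Gain, two looks (points) | Gain if not balanced within strata (points) |
|---|---|---|---|---|---|
| 0 | 0 | 0 | 0.042 | 0 | 0 |
| 10 | 0.7-4.9% | 0.2-1.1 | 0.038-0.0415 | 0.2-0.8 | 0.1-1.7 |
| 20 | 2.6-19.8% | 0.8-4.5 | 0.027-0.040 | 0.7-3.4 | 0.6-6.7 |
| 30 | 5.9-44.4% | 1.9-10.2 | 0.010-0.0375 | 1.7-7.8 | 1.3-14.8 |

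The two-look column uses the printed boundaries with correlation √(37/73), and covers binding and non-binding futility. The 10.2 needs a gap of 30, half the cases open and an SD near 27 together. In the last column the plain test is not conservative; the gain there comes from removing chance imbalance.

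**Simulation checks (100,000 trials per setting).**
- Direction: with SD 22.5, 40% of patients in one stratum and 10% of variance explained by it, the plain test's error was 0.036 (formula 0.034). With the stratum in the model it was 0.043.
- Cost when there is no gap (SD 30, p 0.2): power 60.75% without and 60.74% with the stratum, both against a t reference. Using t rather than Z itself gives up about 0.3-0.5 points.
- Variance estimator at the first look (37 per arm, nominal 0.042): model-based with t gave an error of 0.041-0.042, uncorrected robust (HC0) with Z 0.047-0.048, and HC3 with t 0.039.
- Bounded 0-100 outcome, gap 20, p 0.2: error of the adjusted model 0.041 at 73 per arm and 0.039 at 37; power 61.0% to 63.5% at 73 per arm.

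**The case against.** The case for leaving this alone has substance. It is a matter of efficiency, not validity: at the SD of 22.5 that reproduces the plan, the plain test's power does not drop below the planned 83%. Prognostic value is not documented. Conservatism also needs balance within strata, and section 9.1 describes no blocking.

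The low SD is back-solved as well. The printed boundaries give 81.9-83.3% power if the outcome is treated as a proportion, 67% against 57% with margin -10%, and that corresponds to an SD near 49. At SD 49.5 the gains at true equality are only 0.2-0.3, 0.8-1.3 and 1.9-3.0 points for gaps of 10, 20 and 30. If the mattress were truly 10 points better and the SD 22.5-30, the gain would be at most about 0.2 points, because power is already about 99%. Finally, a stratified Z test would also close the gap and would stay closer to the named test.

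All of this limits the size, and it stands. It does not remove the point. The plan's own hypothesis is equal effectiveness, so true equality is the relevant case. Without blocking, adjustment still gains power. With no gap it costs almost nothing. The freedom to choose after seeing data does not depend on the size of the gain.

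**Conclusion.** The concern holds. The plan stratifies on surgery type and is silent on its use in the analysis. Given balance within strata and a prognostic surgery type, a plain test is conservative. The gain from adjusting is nil with no gap, about 1 point or less at a gap of 10, and 1.9-10.2 points at a gap of 30, all under an assumed SD and share of open cases. No false claim of non-inferiority results. The change should be made because it is nearly free and closes a choice that could otherwise be made after the data are seen; the trial is not invalid without it.

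A separate inconsistency is not cured by adjustment: the printed boundaries give an overall one-sided error of 0.059 (binding futility) or 0.062 (non-binding), against the stated 0.042.

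**What to change.** Add two sentences to section 11.0.

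1. The primary analysis is a linear model of each patient's endpoint percentage on arm and surgery-type stratum as randomised, with the model-based standard error and a t reference. If a robust estimator is preferred, name it and its small-sample correction.
2. Non-inferiority is judged by comparing the lower one-sided limit for mattress minus forced air with -10 percentage points, using the same statistic, expressed on the Z scale, at both looks.

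Take the stratum from the randomisation table, not from the circled item on the form, so that a change of surgery type after randomisation does not alter it.

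The cost is those two sentences and no new data. If the gap is zero, power falls by at most 0.04 points compared like for like. Against a plain Z test the net change can be slightly negative at small gaps, because the t reference gives up 0.3-0.5 points. The mismatch between 0.042, 83% and the printed boundaries needs its own correction.
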